Baseline brain metastases (Investigator)	PresentAbsent	This subgroup classifies participants according to whether or not they have target or non-target lesions in the brain as per investigator assessment. This information is collected on the "Tumor Assessment (according to RECIST 1.1) – Target Lesions" and "Tumor Assessment (according to RECIST 1.1) – Non-target Lesions" eCRF pages at baseline.
Histopathological classification	AdenocarcinomaSquamousOther	This information is collected in the "Histology" eCRF page.

Subgroup	Subgroup level	Definition/ Derivation
Clinical stage at study entry	AdvancedMetastatic	This information is collected in the "Disease History" eCRF page. The TNM classification at study entry will be used to derive the subgroup levels. See details in Section 18.2.
Time from metastatic disease diagnosis to first dose	 < 6 months ≥ 6 months 	The date of documented metastatic disease diagnosis collected in the "Disease History" eCRF page will be used.
Duration of prior osimertinib	 < 12 months ≥ 12 months 	Duration of prior osimertinib therapy (months) as first and only prior anti-cancer therapy. See Section 11.5 for more details.
Time from disease progression on prior osimertinib to first dose	 < 2 months ≥ 2 months 	Time from disease progression on prior osimertinib therapy as first and only prior anti-cancer therapy to start of study treatment (months). See Section 11.5 for more details.
Mean Gene Copy Number	• < 10 • ≥ 10 • < 8 • ≥ 8	Mean Gene Copy Number resulting from the analysis of tumor tissue samples performed centrally with the FISH test.
MET/CEP7 ratio	• <2 • ≥ 2 • $2-<4$ • ≥ 4	MET/CEP7 (centromere 7) ratio resulting from the analysis of tumor tissue samples performed centrally with the FISH test.
Smoking Status	Current SmokerFormer SmokerNever Smoker	Smoking status derivation can be found in Section 11.6.

9

General Specifications for Data Analyses

This section describes any general specifications not included in subsequent sections.

Presentation of continuous and qualitative variables:

Continuous variables other than PK will be summarized using descriptive statistics, i.e., the number of participants with non-missing values (n), mean, standard deviation, median, 25th percentile (Q1) and 75th percentile (Q3), minimum, and maximum.

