If one or more investigation dates for an evaluation are incomplete but other investigation dates are available, the incomplete date(s) are not considered for calculation of the assessment date and assessment date is calculated as the earliest of all investigation dates (e.g., X-ray, CT-scan).

If all measurement dates for an evaluation have no day recorded, the 1st of the month is used.

If the month is not completed, for any of the investigations for an evaluation, the respective assessment will be considered to be at the date which is exactly between the previous and the following assessment. If both a previous and following assessments are not available, this assessment will not be used for any calculations.

Dates of subsequent anti-cancer therapy

For sensitivity analyses where the start of subsequent anti-cancer treatment is considered

Incomplete dates for the start date of subsequent anti-cancer therapies (drug therapy, radiation, surgery) will be imputed as follows and will be used for determining censoring dates for efficacy related sensitivity analyses:

• If only the day is missing, it will be imputed as the first day of the month unless it results in a date before the end date of study treatment. In that case, the incomplete anti-cancer therapy start date will be imputed as the end date of study treatment.

• If both the day and month are missing, the incomplete anti-cancer therapy start date will be imputed as the end date of study treatment if the subsequent therapy started on the same year as the end of study treatment; otherwise, day and month will be imputed as the 1st of January.

For duration of subsequent anti-cancer drug therapies

Incomplete dates of subsequent anti-cancer drug therapies will be imputed as follows:

- If only the day is missing in the start date, the same rule as for the sensitivity analysis described above will be applied.
- If only the day is missing in the end date, it will be imputed as the last day of the month.
- For both start and stop dates, if the month is missing or the date is completely missing, then no imputation will be done and the duration will be considered missing.

Nicotine consumption

Imputation will be used for the calculation of duration of consumption (years) only.

In case of missing month, it will be imputed as follows:

- Missing month of start date will be imputed as January
- Missing month of end date will be imputed as December

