To convert days, months and years into weeks, please see the conversion factors in Section 9.6. For example, if it is needed to calculate the number of cigarettes smoked per week and it is known that the participant used to smoke 100 cigarettes per month, the following calculation will be performed: 100 / (30.4375/7) = 22.998.

A listing will be produced to present data collected on all the nicotine source options.

Chest X-Ray

A listing will be produced to present the results from chest X-rays performed at screening. The information is collected on the "Chest X-ray" eCRF page.

12 Previous or Concomitant Medications/Procedures

The following analyses will be performed based on the SAF analysis set and presented as indicated in Sections 8.1.1 and 8.1.2.

Concomitant medications are medications, other than study treatment, which are taken by participants any time during the on-treatment periods, see Section 9.3.

Previous medications are medications, other than study treatment, which started before first administration of any study treatment.

A medication may be classified as both concomitant and previous. The respective flags will be derived based on start and end date. To derive these flags in case of missing or partial dates, see Section 9.9.

Concomitant medications from Period 1 and previous medications will be summarized by number and percentage of participants from the "Concomitant Medications Details" eCRF page. ATC-2nd level and PTs will be tabulated as given in the most current version of the WHO-DD dictionary at the time of analysis. If any previous or concomitant medication is classified into multiple ATC classes, the medication will be summarized separately under each of these ATC classes. The summary tables will be sorted by ATC-2nd level and PT in descending frequency of the overall total column. In case of equal frequency regarding drug class (respectively drug name), alphabetical order will be used. In case any specific medication does not have an ATC-2nd level coded term, it will be summarized under the "UNCODED" ATC classification category. Each participant will only be counted once, even if he/she received the same medication at different times.

Any medication recorded on the "Concomitant Medications Details" eCRF page will be listed with an indication of whether the medication was previous, concomitant or both. Concomitant medications will be distinguished according to whether they started in Period 1 or Period 2.

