 - Duration of each regimen of therapy administered after discontinuation of study treatment (months) = (date of end of anti-cancer therapy date of start of anti-cancer therapy + 1) / 30.4375. In case of multiple drugs administered within the same regimen, the earliest start among the start dates and the latest end among the end dates will be considered as regimen start and end dates, respectively. See Section 9.9 in case of incomplete dates. The duration of regimens that are still ongoing will not be calculated.
- Subsequent radiotherapy after discontinuation of study treatment
 - Any subsequent anti-cancer radiotherapy: Yes / No
- Surgery after discontinuation of study treatment
 - o Any subsequent anti-cancer surgery: Yes / No

The listings of subsequent anti-cancer treatments will also be provided as follows. These will include the participant identification number, and all the relevant collected data-fields on the corresponding eCRF pages.

- Listing of subsequent anti-cancer drug therapies
- Listing of subsequent anti-cancer radiotherapy
- Listing of subsequent anti-cancer surgeries

13 Study Treatment: Compliance and Exposure

All summaries and listings related to study treatment compliance and exposure will be based on the SAF analysis set. Data will be presented as indicated in Sections 8.1.1 and 8.1.2.

All dosing calculations and summaries will be based on the "Tepotinib Administration Details" and "Osimertinib Administration Details" eCRF pages. The date of last drug administration will

be taken from the "Tepotinib Termination" and "Osimertinib Termination" eCRF pages for those participants who have discontinued treatment by the cut-off date; whereas, for those participants who are still on study treatment, the last dosing date before or at the cut-off date will be used.

For those participants in the monotherapy arm who switch to the combination treatment, the date of last drug administration of tepotinib for Period 1 (see Table 3) will be the last dose of tepotinib that is > 0 mg before the start of the combination treatment.

A dose of tepotinib will be regarded as being taken on a particular day if the actual dose of tepotinib taken is > 0 mg. Interruptions, compliance, and dose changes are not taken into account for the calculation of duration of therapy. These same rules apply to osimertinib.

The following parameters will be provided in summaries and listings for both tepotinib and osimertinib separately:

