	 Population Level Summary: Median PFS time based on Kaplan-Meier estimates and 95% 2-sided CI Kaplan-Meier estimates 			
	 Sensitivity Analyses: As main estimand, but using Investigator assessment instead of IRC assessment. As main estimand but censoring participants who discontinued treatment due to COVID-19 before occurrence of an event at the time of event. 			
	 Supplementary Analyses: As main estimand and sensitivity analysis, but based on different populations: L+, T+ and/or L+. As main estimand, but considering the start of subsequent anti-cancer therapy as PD (composite strategy), to be repeated also on populations L+, T+ and/or L+. As main estimand and sensitivity analysis, based on tepotinib monotherapy as treatment., to be performed also on populations L+, T+ and/or L+. 			
OS	Endpoint: OS as measured by time from first study intervention to death			
	Population : as primary estimand			
	Treatment: Tepotinib combined with osimertinib, taking subsequent anti-cancer therapy int account			
 Intercurrent Event Strategy: Discontinuation of treatment: ignoring the intercurrent event (treatment-policy strat Start of subsequent anticancer treatment: ignoring the intercurrent event (treatment-strategy) 				
	 Population Level Summary: Median OS time based on Kaplan-Meier estimates and 95% 2-sided CI Kaplan-Meier estimates 			
	 Supplementary Analyses: As main estimand and sensitivity analysis, but based on different populations: L+, T+ and/or L+ 			
HRQoL	Endpoint: Change from baseline in health state as measured by the Visual Analogue Scale (VAS) as a component of the EQ-5D-5L questionnaire; global health status, sub-dimensions of functional scales and symptoms scales as measured by EORTC QLQ-C30; cough, chest pain, dyspnea, fatigue, appetitive and overall severity of symptoms measured by NSCLC-SAQ.			
	Population: as primary estimand			

Endpoint	Estimand Attributes			
	Treatment: as primary estimand			
	 Intercurrent Event Strategy: Discontinuation of treatment: ignoring the intercurrent event (treatment-policy strategy) Start of subsequent anticancer treatment: ignoring the intercurrent event (treatment-policy strategy) 			
	 Population Level Summary: LS Mean changes from baseline analysis for cough, pain and dyspnea (NSCLC-SAQ) General descriptive statistics to summarize values and change from baseline by visit 			

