14.2.3 Duration of Response by IRC and by Investigator

Duration of Response (DOR) will only be evaluated for participants with objective response (as defined in Section 14.1.1).

DOR is the time from when the CR/PR (whichever is first) criteria are first met until PD or death due to any cause, within 126 days of the last evaluable tumor assessment, whichever occurs first (see Eisenhauer EA, et all 2009) (i.e., date of PD/death - date of last evaluable tumor assessment \leq 126).

DOR data will be censored on the date of the last evaluable tumor assessment for participants who do not have an event (PD or death) or for participants with an event more than 126 days after the last evaluable tumor assessment (i.e. date of PD/death - date of last evaluable tumor assessment > 126).

The last evaluable tumor assessment is defined as the last tumor assessment result that is not "NE".

Kaplan-Meier estimates (product-limit estimates) will be presented together with a summary of associated statistics for duration of response: median and corresponding two-sided 95% confidence interval (CI), Q1 and Q3, minimum and maximum. Progression-free rate estimates at 3, 6, 9, 12, 15, 18 months and for every 3 months thereafter as applicable including the corresponding two-sided 95% CIs will also be reported. The CI for the median will be calculated according to Brookmeyer and Crowley (1982) and CIs for the survival function estimates at the above defined time points will be derived using the log-log transformation according to Kalbfleisch and Prentice (1980) (conftype=loglog default option in SAS Proc LIFETEST). The estimate of the standard error will be computed using Greenwood's formula. Kaplan-Meier plots will also be presented.

Categorical summaries of DOR features will be presented for the following items:

- Number of participants with OR
- Duration of response: ≥ 6 months, ≥ 9 months, ≥ 12 months
- Follow-up among responders:
 - \circ participants with ≥ 6 months follow-up from onset of response or event (PD or death) or discontinued treatment < 6 months after onset of response
 - \circ participants with ongoing response with < 6 months duration

Results for DOR as described above will be presented by IRC and Investigator assessments.

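### SAP Section 12 summarises the duration of subsequent anti-cancer drug regimens only for regimens that have ended, so longer regimens drop out preferentially and the summary runs short

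*SAP*

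**What the plan says.** Under subsequent anti-cancer therapy, SAP Section 12 defines the duration of each later drug regimen as end date minus start date plus 1, divided by 30.4375. For a multi-drug regimen it takes the earliest start and the latest end among the drugs. It then says: "The duration of regimens that are still ongoing will not be calculated".

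The rules around this sentence are:

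- **Population.** SAP Section 12: "The following analyses will be performed based on the SAF analysis set".
- **Summary method.** The general rule in SAP Section 9 applies: "Continuous variables other than PK will be summarized using descriptive statistics, i.e., the number of participants with non-missing values (n), mean". No censoring and no count of ongoing regimens is specified for this variable.
- **Incomplete dates.** Under SAP Section 9.9, if the month or the whole date is missing, "then no imputation will be done and the duration will be considered missing".
- **Other output.** Ongoing regimens still count in the number, type, intent and drugs of subsequent therapy, and they appear in the listing. They only contribute no duration.

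The same SAP treats comparable durations differently. For duration of study treatment, Section 13 says that "for those participants who are still on study treatment, the last dosing date before or at the cut-off date will be used". For duration of response, Section 14.2.3 says that "Kaplan-Meier estimates (product-limit estimates) will be presented together with a summary of associated statistics for duration of response".

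**The concern.** Whether a regimen is ongoing at an analysis depends on how long it lasts. Leaving out ongoing regimens turns right-censored data into complete cases, and the regimens kept are those short enough to have finished. On the natural reading of the multi-drug rule, one continuing drug leaves the whole regimen without an end, so it drops out too.

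This row is the only planned summary of how long later therapy lasted. In the estimands table of SAP Section 14, the treatment attribute for OS begins "Tepotinib combined with osimertinib, taking subsequent anti-cancer therapy" and goes on to say that this therapy is taken into account. A reader who wants to know what followed study treatment will look at the row and find a duration that is too short. The reader also cannot compare it fairly with duration of study treatment, which counts ongoing time. What is at stake is the accuracy of a descriptive table.

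**Working it through.** The plan states no figure for regimen duration, so there is nothing to reproduce. The check covers direction first, then plausible size.

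**Inputs from the documents.** The primary analysis occurs once all globally enrolled participants in the primary set have had 9 months of treatment, died or discontinued (SAP 6.3). The first three run-in participants had completed Cycle 1 by 5 May 2020 (protocol 4.3). The last global participant started on 28 June 2022 (SAP 7), and nine months later is 28 March 2023. The Chinese extension enrolled until 7 November 2022 (SAP 7), and SAP 8.1 excludes those participants from the mFAS but not from the SAF. At the final analysis up to one third of participants may be alive (SAP 6.5). Ongoing regimens are therefore possible at both analyses.

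**Assumptions.** Regimen duration T has a true median of 5 months, with an exponential or a Weibull (shape 1.5) distribution. Regimen starts are uniform over the W months before the analysis, independent of T.

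**Direction.** A regimen of length t has ended by the analysis with probability 1 − t/W for t ≤ W, and 0 beyond. The density of completed durations is proportional to f(t)(1 − t/W). This weight falls with t, so the completed-only median lies below the true median. Recently started regimens of any length are also lost.

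**Size, exponential case.** λ = ln 2 / 5 = 0.1386 per month.

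- Share ongoing = (1 − e^(−λW)) / (λW).
- Share of all regimens completed with duration ≤ m: G(m) = (1 − e^(−λm)) − (1/W)[(1 − e^(−λm))/λ − m·e^(−λm)].
- The completed-only median solves G(m) = G(W)/2.

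For W = 24: λW = 3.327, so the share ongoing is (1 − 0.0359)/3.327 = 0.290. G(W) = 0.710 and half of that is 0.355. At m = 3.45, e^(−λm) = 0.620 and G = 0.380 − (2.743 − 2.138)/24 = 0.355. The completed-only median is 3.45 months, or 69% of 5.

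The Weibull case (scale 5/(ln 2)^(1/1.5) = 6.38 months) uses the same weight, integrated numerically.

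| W (months) | Exponential: ongoing | Median (months) | % of truth | Weibull 1.5: ongoing | Median (months) | % of truth |
|---|---|---|---|---|---|---|
| 9 | 57.1% | 1.97 | 39.5 | 57.5% | 2.87 | 57.5 |
| 12 | 48.7% | 2.40 | 48.0 | 46.2% | 3.39 | 67.7 |
| 18 | 36.8% | 3.03 | 60.6 | 31.9% | 3.98 | 79.6 |
| 24 | 29.0% | 3.45 | 69.0 | 24.0% | 4.28 | 85.5 |
| 36 | 19.9% | 3.95 | 79.0 | 16.0% | 4.54 | 90.9 |

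Other true medians, exponential, W from 9 to 24: 55% to 81% of truth for 3 months, and 27% to 55% for 8 months.

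**Simulation check.** Regimens were simulated for true medians of 3, 6 and 9 months, W of 6, 12, 18 and 24, and both shapes: 24 scenarios of 400,000 regimens each. The completed-only median was too short in all 24, by about 8% to 82%, with 14% to 87% of regimens ongoing. Among ongoing regimens, 15% to 42% would have ended below the true median. A Kaplan-Meier median with ongoing regimens censored returned the true value to within about 0.03 months wherever it was estimable. It was not estimable for true medians of 6 or 9 months with a 6-month window.

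**The case against.** The case for leaving the rule alone has five parts.

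1. **No endpoint is affected.** Regimen duration enters no calculation of ORR, DOR, PFS or OS. The OS estimand uses a treatment-policy strategy, no hypothesis is tested (protocol 9.1), and OS is presented for the combination arm only (SAP 14.2.6). This stands in full. A reader might infer that an understated duration credits too much survival to tepotinib plus osimertinib. The documents do not support that: no planned analysis uses this row to apportion survival, and the same table reports best response to later therapy.
2. **Ongoing regimens remain visible.** They are in the counts and the listing, and the rule is stated openly. This stands, but neither output corrects the duration or puts the number ongoing beside it.
3. **Not only the longest regimens are lost.** This stands. Recently started regimens go too, so the accurate word is preferentially.
4. **The size is assumed.** This stands. Enrolment ran for more than two years, so some regimens will have started long before the primary analysis, and a wide window may be the better description. The bias is then smaller, but the direction does not change while any regimens are ongoing.
5. **Censoring is not trivial here.** SAP 9.7 derives last contact only for participants not known to have died, SAP 9.1 applies no cut-off at the final analysis, and survival contact is every 3 months, possibly by telephone. These points shape the wording of the fix. They do not justify dropping the ongoing regimens. Nor is Kaplan-Meier the only acceptable choice: Section 13 does not use it for study treatment.

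**Conclusion.** The point holds as a minor defect in a descriptive table. Followed as written, SAP Section 12 gives a duration of subsequent drug regimens that is biased short whenever some are ongoing, and no other section offsets this.

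The size depends on the share ongoing, which the documents do not give. For an assumed true median of 5 months, the completed-only median is about 40% to 69% of the truth with exponential durations and start windows of 9 to 24 months. With a 36-month window it is about 79% (exponential) to 91% (Weibull, shape 1.5). The bias is larger at the primary analysis than later. All these figures assume uniform regimen starts that are independent of duration. They illustrate the problem and do not predict this trial's result. No efficacy endpoint is biased.

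**What to change.** In SAP Section 12, replace the sentence "The duration of regimens that are still ongoing will not be calculated" with:

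> *Ongoing regimens without an end date are included and censored at the date of last contact (on or before the cut-off where one applies). For participants who died with no recorded end date, the regimen is taken to end at the date of death. Duration by regimen number is summarised by the Kaplan-Meier median with 95% CI, together with the number of regimens ongoing. Any summary without ongoing regimens is labelled 'completed regimens only'.*

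The Section 9.9 rule for incomplete dates can stay for regimens known to have ended.

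Cost: one small extra table and no new data, since later therapy is already recorded until death (protocol 8.1) and date of last contact is already derived (SAP 9.7). Two limits should be accepted: the median may not be estimable for later regimens with few participants, and the censoring date is only as precise as the 3-monthly survival contact. If the sponsor does not want a Kaplan-Meier table, the minimum is the label and the number ongoing beside the existing summary. That discloses the bias but does not remove it.

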14.1 Primary Endpoint: Objective Response by IRC

14.1.1 Derivation and analysis

BOR will be assessed based on reported overall responses at different evaluation time points from the study treatment start date until documented disease progression in accordance with RECIST v1.1, taking requirements for confirmation into account as detailed below. Clinical deterioration will not be considered as documented disease progression. The date of the overall response assessment is the earliest date for imaging of target, non-target and new lesions of images taken at that response assessment.

BOR Based on Confirmed Responses:

- CR = at least two determinations of CR at least 4 weeks (28 days) apart (with no PD in between)
- PR = at least two determinations of PR or better (PR followed by PR or PR followed by CR) at least 4 weeks (28 days) apart (and not qualifying for a CR), with no PD in between
- SD = at least one SD assessment (or better) ≥ 12 weeks (84 days) after the start date of study treatment (and not qualifying for CR or PR)
- $PD = PD \le 90$ days after start date of study treatment (and not qualifying for CR, PR or SD)
- Not Evaluable (NE): all other cases.

There may be uncommon situations where the above rules might need further explanation. Some of these cases are listed below together with the BOR value that should be assigned:

- SD can follow PR only in the rare case that tumor increases by less than 20% from the nadir, but enough that a previously documented 30% decrease from baseline no longer holds. If this occurs, the sequence PR-SD-PR is considered a confirmed PR. A sequence of PR-SD-SD-PD would be a best response of SD if the minimum duration for SD definition has been met.
- When an unconfirmed PR or CR is assessed at least 12 weeks after the start date of study treatment with no PD before, the best response would be SD.
- When there is an assessment of SD, PR or CR within 12 weeks from the start of study treatment followed by a PD after 90 days, the best response would be NE.

Participants are defined as having an Objective Response (OR) if they achieved either a confirmed BOR of CR or PR according to RECIST v1.1 from first administration of study treatment to first observation of PD.

The OR rate (ORR) is the proportion of participants with OR in the analysis set.

No formal statistical hypotheses will be tested.

The number and percentage of participants with BOR of confirmed CR, confirmed PR, SD, PD, and NE as well as the number of participants achieving objective response, the ORR and the corresponding 2-sided exact Clopper-Pearson 95% CI will be presented.

BOR and ORR results will be presented for all participants in the mFAS.

Spider plots will show the percent change in the sum of target lesion diameters (sum of longest diameters for non-nodal lesions, short axis for nodal lesions) over time. Different line patterns will distinguish time on and off-treatment. For the participants in the monotherapy arm who switched to the combination treatment, an additional spider plot will be produced presenting the percent change in the sum of target lesion diameters after the switch.

In addition, waterfall plots will show the percent change in sum of target lesion diameters between baseline and the best post-baseline assessment for each participant. Different colors will illustrate the BOR.

The data collected in the "Cytological Assessment for IRC Details" and "Neurological Assessment" eCRF pages will be listed for the FAS.

14.1.2Sensitivity Analyses

A sensitivity analysis will be conducted in which only tumor assessments performed before the start of any subsequent anti-cancer therapies (i.e., anti-cancer drug treatment, surgery or radiotherapy) will be considered in the assessment of BOR. If a tumor assessment was performed on the same day as start of new anti-cancer therapy, it will be assumed that the tumor assessment was performed prior to the start of the new anti-cancer therapy, therefore the tumor assessment will be included in the assessment of BOR. If only partial dates are known for the start of other anti-cancer treatment or procedures, the imputation rules described in Section 9.9 should be followed. This analysis will be performed for the combination arm only.

A further sensitivity analysis will be performed to display BOR and ORR for the FAS for both treatment arms overall (i.e., with no split by MET amplification test result).

